8 INVESTIGATIONAL PRODUCT

8.10verview

NKA is an injectable product composed of SRC formulated in a Biomaterial (gelatin-based hydrogel). A detailed description of SRC and NKA and the manufacturing process is provided in the IB. A brief description of the process is described below, divided into three steps:

Biopsy: Renal cortical tissue obtained via kidney biopsy is sent to Twin City Bio LLC, Winston Salem, North Carolina, for manufacturing.

Selection of SRC: Renal cells are isolated from the kidney tissue by enzymatic digestion and expanded using standard cell culture techniques. Cell culture medium is designed to expand primary renal cells and does not contain any differentiation factors. Harvested renal cells are subjected to density gradient separation to obtain SRC which are composed a selected population of renal cells, cells well known for their regenerative potential (Humphreys et al., 2008).

Formulation: Gelatin-based hydrogel biomaterial is used to formulate SRC into NKA. Porcine gelatin is dissolved in buffer to form the thermally responsive hydrogel. This hydrogel is fluid at room temperature but gels when cooled to refrigerated temperature (2-8°C). SRC is formulated

```
Confidential
```

in this gelatin-based hydrogel biomaterial to improve both cellular stability during transport and injection into the kidney cortex.

8.2 Procurement and Manufacture of NKA

NKA will be manufactured in a GMP facility at Twin City Bio LLC in Winston-Salem, NC.

8.2.1 Biopsy: Procurement of Renal Tissue

Those patients enrolling in this clinical trial after participation in the previous single-dose clinical trial will be injected with SRC cells obtained from their initial biopsies. Biopsy samples were obtained for these patients in a Phase 1 trial and maintained in a frozen state. These autologous samples will be used to generate the second dose of NKA that the patients are to receive under this protocol. If there are not enough SRC cells obtained in the remaining sample, patients will be allowed to undergo another biopsy to prepare their second NKA injection dose. Patients who are enrolling in a clinical trial of NKA for the first time will have SRC cells prepared from kidney biopsy tissue obtained according to the usual standard of care procedures.

8.2.2 Product for Injection

Once the biopsy material is received at Twin City Bio LLC, the NKA product will be labeled and strict documentation measures will insure product traceability is maintained. The site will notify Twin City Bio LLC of the date for injection and, following the pre-injection visit, of continuing patient eligibility so that manufacturing can adjust the in-process freezing step to accommodate the date of surgery. If the patient still qualifies, cells will be thawed, NKA manufactured and subsequently shipped. If the patient does not qualify, the PI should notify Twin City Bio LLC staff and renal cells will not be thawed for shipping. In this case, the PI, Twin City Bio LLC, and RegenMed (Cayman) Ltd. staff will discuss available options including, for example, thawing of cells at a later date.

Product will be packaged in sterile packaging in a 10 mL syringe for shipment and shipped to the address provided by the site. It is the responsibility of the site to ensure NKA shipments can be delivered directly to site personnel so that product injection is not delayed. NKA in the syringe must be warmed to $26.5 \pm 1.5^{\circ}$ C before injection, in order to liquefy the gelatin-based hydrogel component of NKA. Instructions for warming the product will be provided in the Study Reference Manual. Detailed injection procedures can be found in Section 8.2.2.

Renal cells/SRC that were frozen but not used to manufacture NKA will be stored at Twin City Bio LLC's GMP facility until the End-of-Study Visit for the patient. At that time, if the cells have not been used and it is determined that they are no longer needed for that patient, then they will be designated for RegenMed (Cayman) Ltd. use and will be used for growth optimization, stability assessments, and other process improvement studies. Some process improvement studies may include assessment of biomarker panels to assist in further characterization of specific cellular phenotypes present in each NKA sample. Renal cells/SRC will be kept for a maximum of 5 years. During the informed consent process, the patient will be alerted to the planned future use of his/her cells. If the patient does not want his/her cells to be used for process improvement research, then during the informed consent process, he/she may request that the cells be destroyed after he/she has completed the study.

8.3NKA Dose

In nonclinical studies, harvested kidneys were weighed directly; dose was calculated based on the average weight of a dog or rat kidney. Using the results from nonclinical studies, each patient will receive a dose of 3.0×10^6 SRC/g KW^{est}. For patients in the study, the dose of NKA will be based on kidney volume calculated using MRI. As described in the literature, volume measurements of the kidney in mLs obtained by different methods are approximately 92 - 97%of dry weight measurements in grams obtained by measuring isolated organs trimmed of perirenal fat. Therefore, as a conservative estimation, doses of NKA will be calculated using a conversion of 1 g equals 1 mL. Using this ratio represents the safest approach as it guarantees patients will not receive doses higher than corresponding doses in animal studies. Dosing volumes for a range of kidney weights are shown in Table 7 below. The maximum volume for any patient will be 8.0 mL; that is, if any subject has a left kidney with a calculated weight ≥ 259 g, then that subject will receive 8 mL of NKA.

Estimated Kidney Weight (g KW ^{est})		Dose Volume	SRC Delivered	
Median Weight (g)	Weight Range (g)	(mL)	(cell number; x 106)	
100	95 - 108	3	300	
117	109 - 125	3.5	350	
133	126 - 141	4	400	
150	142 - 158	4.5	450	
167	159 - 175	5	500	
183	176 – 191	5.5	550	
200	192 - 208	6	600	
217	209 - 225	6.5	650	
233	226 - 241	7	700	
250	242 - 258	7.5	750	
	>259	8	800	

Table 7: NKA Dosing Paradigm

8.4Accountability

Investigational product will be sent prepackaged in a sterile syringe. The site should verify the subject information matches the subject to be injected. If required by site practices, the site pharmacy may add a site-specific label prior to transport to the operating room. The site should also verify the amount of NKA to be injected based on the kidney weight determined by MRI imaging at screening. During injection, the amount of NKA delivered should be documented in source documents including estimates of the amount of product that leaked out of the kidney following injection, if any.

Following injection, any excess NKA remaining in the syringe will be disposed of in the surgical suite immediately following surgery according to site standard practices.

9 STUDY DESIGN

An overview of the study flow is shown in the diagram below.

After patients have signed the ICF, they should be screened for entry into the study. Screening assessments include laboratory assessments, physical examination, and an ECG and MRI study, all of which must be performed before the biopsy is taken. If the patient meets all I/E criteria, a biopsy of the left/right kidney should be taken within 45 days of the first screening assessment. During the biopsy procedure, two tissue cores should be collected and sent to RegenMed (Cayman) Ltd. for manufacture of NKA. If the patient experienced significant AE's/SAE's following biopsy (e.g., excessive bleeding, development of AV fistula) that, in the opinion of the PI would preclude safe injection, then the patient should be discontinued from the study. Biopsy samples that were obtained from previously enrolled patients in a Phase 1 trial and maintained in a frozen state will be used to generate the second dose of NKA that the patients are to receive

under this protocol. If there are not enough cells after thawing then these patients will be allowed to have the biopsy procedure completed for this study.

One week after receipt at Twin City Bio LLC's GMP facility in North Carolina, USA, RegenMed (Cayman) Ltd. will notify the site if the tissue received was of sufficient size and quality for manufacture of NKA. If results are positive, the site should confirm the scheduled date of injection. If the biopsy specimen is not able to be used for manufacture of NKA (for whatever reason), the patient should be discontinued from the study.

Ten to 14 days before the scheduled injection, the patient should report to the clinic for a preinjection qualification visit including final review of I/E criteria and a renal scintigraphy study. If the patient is still eligible for injection, the site will notify Twin City Bio LLC to manufacture NKA product from frozen renal cells. On the day of injection (Day 0), the patient should be admitted to the hospital and receive an NKA injection into the left (i.e., biopsied) kidney. For injection, the kidney will be accessed either (a) laparoscopic approach, or (b) using a percutaneous approach. The patient will remain in the hospital for two to four nights following the laparoscopic procedure, or 0-1 night following the percutaneous procedure, for observation and safety assessments. The patient should not be discharged until any procedure- and/or product-related AE's which may have occurred have stabilized or resolved.

Post-injection Follow-up: Subjects will return to the clinic for follow-up safety assessments on Days 7, 14, and 28 post-injection and at 3, 6, 9, and 12 months post-injection. At 6 months post-injection, post-treatment MRI and renal scintigraphy studies will be conducted. After patients complete the 6 month efficacy visit, they will be considered for a second NKA injection. Patients receiving a second dose will follow the same follow up visits that occurred after first dose. Patients 6 month post first injection visit will serve as the patients 14 to 10 day pre- second injection visit. Patients will return for their second injection and at 2, 3, and 6 months post-second injection. Patients will be followed up to 18 months in the post follow up phase with 6 months after first NKA injection and 12 months after second NKA injection. Refer to the time and events schedule on page 14 for additional post follow up time points. Subjects will complete an End-of-Study visit when they discontinue from the study or (for those who complete the study) at 18 months post-second injection.

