- 22. Patients with bleeding disorders that would, in the opinion of the Investigator, interfere with the performance of study procedures; patients taking coumarins (e.g. Warfarin) or other anticoagulants (e.g. enoxaparin or direct thrombin inhibitors).
- 23. Any circumstance in which the investigator deems participation in the study is not in the subject's best interest.
- 24. Use of any investigational product within 3 months of the injection without receiving prior written consent of the Medical Monitor.

Number of Sites: Up to 10 clinical centers will be included in the study.

Study Duration: 18 months NKA injections follow up followed by 24 month long term follow up for a total study duration of 42 months.

Study Enrollment: Up to 30 subjects undergoing NKA injection will be enrolled into the study. Patients who have received a single injection of NKA under previous research protocols may enroll in this clinical trial to receive a single additional injection. Patients who have never received an NKA injection may enroll in this clinical trial for up to a total of two (2) NKA injections, temporally spaced at least 6 months apart. All biopsies are to be taken from a single kidney, and all NKA injections are to be given into the kidney that was biopsied. Patients who complete screening procedures satisfying all I/E criteria will be enrolled into the study immediately prior to the injection. Patients who do not meet all criteria before injection will be considered screen failures. Once a patient has been injected, the patient will have completed treatment and every effort should be made to ensure the patient completes all follow-up visits. Injection dates for the first 3 patients receiving their second NKA injection will be staggered by a minimum of 3 week intervals to allow for assessment of acute adverse events and other safety parameters by the DSMB. Subsequent second injections will continue to be staggered so as to occur no less than 3 weeks apart, but individual DMSB review will not be required. At the completion of the follow-up visits, patients will continue in a long-term follow-up study. Patients will be followed for a total of 36 months following the last NKA injection under this protocol, whether the first or second injection.

Investigational Plan:

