NKA Dose: Kidney weight of the target/recipient kidney will be estimated from the results of the MRI taken during Screening. Using the preclinical studies as a guideline, the dose of NKA for this study is 3×10^6 cells/g estimated kidney weight (g KW^{est}). Since the concentration of SRC per mL of NKA is 100 x 10⁶ cells/mL, the dosing volume would be 3 mL for each 100 g or 6 mL for a 200 g kidney. Based on this dosing paradigm, the following doses of NKA would be administered:

Estimated Kidney	Weight (g KW ^{est})	Dose	SRC Delivered						
Median Weight	Weight Range	Volume	(cell number; x						
(g)	(g)	(mL)	106)						
100	95 - 108	3	300						
117	109 - 125	3.5	350						
133	126 - 141	4	400						
150	142 - 158	4.5	450						
167	159 - 175	5	500						
183	176 – 191	5.5	550						
200	192 - 208	6	600						
217	209 - 225	6.5	650						
233	226 - 241	7	700						
250	242 - 258	7.5	750						
	>259	8	800						

Safety Monitoring: While unforeseen adverse effects may occur, the greatest recognized risk to subjects enrolled into the study is hemorrhage following the injection procedure. Therefore, precautions have been taken to minimize the risk of excessive bleeding. Patients with abnormal laboratory values predictive of an increased risk of bleeding will not be eligible for the study. Hemoglobin/hematocrit will be monitored a) before, b) 4 hours after, and c) the day after each procedure.

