6.5.3 Selection of Kidney for Biopsy/Injection

Laparoscopic surgical techniques can be used to access either the right or left kidney. However, the left kidney is more readily accessible and is most often accessed during nephrectomies, hence the first surgical team had more experience with accessing the left kidney, and the initial patients enrolled underwent left kidney biopsy and left kidney NKA injection. Patients previously enrolled may have a second NKA injection in the left kidney. Newly enrolled patients may have either the left or right kidney biopsied. In any case, the NKA injection should be made into the kidney that was biopsied.

6.6Benefit: Risk Assessment

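### Left-kidney wording remains in the injection instruction (section 9) and the 8 mL rule (section 8.3), although new patients may be biopsied and injected on the right

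*Combined protocol and SAP*

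**What the plan says.** **Side of biopsy.** Section 6.5.3 explains that the first patients were biopsied and injected on the left. It then opens the choice: "Newly enrolled patients may have either the left or right kidney biopsied". Section 9 (first part) and section 12.5.1 also allow the biopsy on either side.

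**Side of injection.** Section 6.5.3 continues: "In any case, the NKA injection should be made into the kidney that was biopsied". The synopsis, under Study Enrollment, agrees: "all NKA injections are to be given into the kidney that was biopsied". The synopsis repeats this under Investigational Plan (Injection), and the percutaneous procedure in section 12.5.2 has the operator establish which kidney was biopsied and plan the approach to that one. A later paragraph of section 9, however, says that on Day 0 the patient should "receive an NKA injection into the left (i.e., biopsied) kidney".

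**Kidney that sets the dose.** The synopsis, under NKA Dose, says: "Kidney weight of the target/recipient kidney will be estimated from the results of the MRI taken during Screening". Section 8.3 gives the dose per gram of estimated kidney weight, and Table 7 turns it into volumes; neither names a side. Section 8.3 then states the cap, "The maximum volume for any patient will be 8.0 mL", and explains it with a clause that does name one: "if any subject has a left kidney with a calculated weight ≥ 259 g, then that subject will receive 8 mL of NKA". Section 12.5.2 gives the volume rule and the 8 mL maximum without a side.

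**The concern.** Both left-kidney wordings stand in current text that sites are meant to follow. For a returning Phase 1 patient treated on the left they do no harm. For a new patient biopsied on the right, the section 9 instruction contradicts itself, because the left kidney is not the biopsied one. The section 8.3 clause would then read the 8 mL trigger from the kidney that is not injected. At stake are which kidney is injected and, in some patients, how much product is given. In an open-label study of up to 30 patients, each treated according to the weight of one kidney, the protocol should give one answer to each question.

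**Working it through.** **1. Side, passages compared for a right-biopsied patient**

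| Place | Kidney to inject |
|---|---|
| Synopsis, Study Enrollment | Biopsied kidney: right |
| Synopsis, Investigational Plan (Injection) | Biopsied kidney: right |
| Section 6.5.3 | Biopsied kidney: right |
| Section 12.5.2, percutaneous procedure | Biopsied kidney: right |
| Section 9, Day 0 paragraph | Left, glossed as the biopsied kidney: no consistent reading |

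**2. Reproducing the dose table**

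Inputs: 3.0 million cells per g (section 8.3) and 100 million cells per mL (synopsis, NKA Dose).

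Volume = 3.0 × weight / 100 = 0.03 × weight (g), rounded to the nearest 0.5 mL.

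At the ten median weights in Table 7 (100, 117, 133, 150, 167, 183, 200, 217, 233 and 250 g), the unrounded volumes are 3.00, 3.51, 3.99, 4.50, 5.01, 5.49, 6.00, 6.51, 6.99 and 7.50 mL. Rounded, they match all ten table entries (3 to 7.5 mL). At the 259 g threshold in section 8.3, 8 mL is 800 / 259 = 3.09 million cells/g. The table is sound; only the side is in question.

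**3. When the literal left-kidney clause changes the volume (right kidney injected)**

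| Left kidney | Right kidney | Table 7, right kidney | Literal clause | Differ? |
|---|---|---|---|---|
| < 259 g | < 259 g | by table | clause not triggered; by table | No |
| < 259 g | ≥ 259 g | 8 mL | clause not triggered; table gives 8 mL | No |
| ≥ 259 g | ≥ 259 g | 8 mL | 8 mL | No |
| ≥ 259 g | < 259 g | 7.5 mL or less | 8 mL | Yes |

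Only one of the four combinations gives a conflict.

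**4. Size of the conflict in that combination**

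The documents contain no left and right kidney weights, so the weights below are assumptions. The left kidney is set at 260 g, just above the threshold, and the right is varied. Cells per gram = volume × 100 / right-kidney weight.

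| Right kidney (g) | Table 7 (mL) | Literal clause (mL) | Difference (mL) | Table 7 (million cells/g) | Literal clause (million cells/g) |
|---|---|---|---|---|---|
| 258 | 7.5 | 8 | 0.5 | 750/258 = 2.91 | 800/258 = 3.10 |
| 241 | 7 | 8 | 1 | 700/241 = 2.90 | 800/241 = 3.32 |
| 225 | 6.5 | 8 | 1.5 | 650/225 = 2.89 | 800/225 = 3.56 |
| 200 | 6 | 8 | 2 | 600/200 = 3.00 | 800/200 = 4.00 |

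For scale, rounding to 0.5 mL already lets Table 7 vary around 3.0, up to 350/109 = 3.21 million cells/g at the bottom of its second row. The first case (3.10) lies inside that spread; the other three do not.

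**The case against.** The strongest reply is that this is leftover wording from a left-sided Phase 1 study and that the intent is plain. On side, that largely stands. The section 9 sentence carries its own gloss, the same section earlier allows either side for the biopsy, and the synopsis, section 6.5.3 and the percutaneous procedure all point to the biopsied kidney. A reader might infer that the protocol as a whole sends right-biopsied patients to the wrong kidney; it does not. What remains is that an instruction for the day of injection cannot be obeyed as written, and that the laparoscopic text in section 12.5.2 has no counterpart to the percutaneous step of establishing which kidney was biopsied.

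On dose, a reader might infer that section 8.3 doses every right-sided patient by the other kidney. That is not supported either. The per-gram rule, Table 7 and the cap itself name no side, the synopsis names the recipient kidney, and the left kidney appears only in the clause that explains the cap. The check in section 8.4, where the site verifies the amount against the MRI kidney weight, helps in general. It names no side, so it does not settle the one combination that conflicts.

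Three further inferences go beyond the documents:

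- **Number of patients.** If all 7 Phase 1 patients return and 30 are injected, 30 − 7 = 23 are new. That counts new patients, not right-sided ones, and 30 is a maximum.
- **A one-third excess.** The step from 3.0 to 4.00 million cells/g holds for an assumed 260 g and 200 g pair. It is not an expected size.
- **Endpoint coding and case report form.** Nothing shows that the left-kidney wording affects how split function or kidney volume is coded. The form is not among the documents, so it cannot be said to lack fields for side.

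**Conclusion.** The inconsistency is real and sits in current text, but it is narrow. On side, one sentence in section 9 conflicts with the rest of the plan for any right-biopsied patient, and the intent can be recovered. On dose, one clause in section 8.3 conflicts with the synopsis and Table 7 only for right-injected patients with a left kidney of at least 259 g and a right kidney below 259 g. Under the assumed weights the gap is 0.5 to 2 mL; a more unequal pair would widen it. How many patients would be right-sided, and how many of those would fall in this combination, cannot be determined from the documents and could be none. No sample size, power or error rate is involved. The point merits correction because it concerns which kidney is treated and with what volume, and because correcting it costs very little. This review takes no position on which rule should apply.

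**What to change.** Reconcile the Day 0 paragraph of section 9 and the 8 mL clause of section 8.3 with the synopsis (Study Enrollment, Investigational Plan and NKA Dose), section 6.5.3, the biopsy text in sections 9 and 12.5.1, and the injection text in section 12.5.2. After that, one consistent statement should govern the side of injection, and one should govern which kidney's weight sets the volume. The content of both rules is for the sponsor to decide.

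If they are not already captured, record three items for each injection: the side of the biopsy, the side of the MRI weight used for dosing, and the side injected. Agreement among them can then be checked whichever rule is adopted.

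The cost is two wording corrections and, at most, three data fields with one consistency check. No analysis changes.

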10 STUDY POPULATION

10.1 Eligibility Criteria

Eligibility criteria should be assessed at Screening. In addition, unless otherwise noted for the specific criterion, eligibility criteria should be also be reviewed before the biopsy and at the Day -10 to -14 pre-injection visit.

Up to 30 subjects will be enrolled in this study, including subjects previously injected in either Phase 1 trial. Note that a subject will be considered enrolled into the study at the time of injection.

